2.6 Sample size

For the primary research outcome, a sample size of 120 index cases per arm will provide 80% power. We anticipate that the attack rate for within household transmission will be approximately 85% in the control arm and 75% in the intervention arm. Under these assumptions, in a cluster randomised trial with a binary outcome, assuming an intracluster correlation coefficient of 0.2, an alpha of 0.05 (two sided), and assuming 3 additional household members (in addition to the index case) we have 80% power to detect a reduction in transmission to household contacts. The requisite sample size is then 120 index cases and 360 household contacts per arm. Allowing for 10% loss to follow-up this is increased to 134 index cases (households) per arm, approximately 536 persons per arm. We plan to enroll 268 households and approximately 1072 individuals.

If the household size is 2 additional people, rather than 3, and with all other assumptions the same, we would require 334 households and approximately 1002 individuals. The target sample size for the primary outcome is 1100 individuals enrolled.

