The analysis will follow the intention to treat principle, but only some households will be eligible for this objective. A household will be eligible if there is at least one participant in the household who tested positive to SARS-CoV-2 by PCR on Day 1 and one participant who tested negative to SARS-CoV-2 by PCR on Day 1, using the health care provider collected swab. It does not matter whether it was the index case or another household member who tested positive. Households where all participants test positive or where all participants test negative will not be eligible for this analysis.

Treatment arms will be compared using generalised linear mixed models (GLM) with infection status as the binary outcome, adjusting for stratification factors (time from positive test to randomisation, whether the index case is a child < 5 years), participant age, inhaled steroid use at baseline, days since symptom onset at randomisation, whether there are children in the household and household size (referred to as the defined baseline covariate set, see Section 3.9), with household as random effect to take the clustering by household into account. Both relative and absolute differences in proportions will be reported with 95% confidence intervals.

Relative differences (risk ratios) between the treatment arms will be calculated using a Poisson regression with robust standard errors in Stata as follows:

xtpoisson outcome i.arm baseline_covariates, re vce(robust) irr

Absolute differences (risk difference) between the treatment arms will be calculated in Stata as follows using a mixed effects GLM with random intercepts: megIm outcome i.arm baseline_covariates || household:, family(bin) link(logit)

The margins statement will be used to compute the risk difference by subtracting the probability of the outcome in the control arm from the probability in the treatment arm margins i.arm, atmeans post lincom _b[1.arm] - _b[0.arm]

Both these models are fairly complicated models to fit and might not converge if sparse data is encountered, given all the baseline covariates included. If the models do not converge, the following strategies will be tried:

- Exclude some of the baseline covariates especially binary covariates, covariates with sparse categories, or covariates with little variability
- Or, fit the following simpler models

Relative differences (risk ratios) between the treatment arms will be calculated in Stata as follows using robust standard errors:

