We will summarise the number of participants in each of the 4 categories of the Likert scale in each treatment arm. A mixed effects proportional odds logistic regression will be used to calculate the overall odds ratio, adjusted for the stratification variables and clustered on household. The assumption of proportional odds will be investigated. If it is violated, we will fit a multinomial regression and calculate an odds ratio for each category.

This analysis will also be repeated in the subgroup of participants who tested positive to SARS-CoV-2 infection at baseline.

The following subgroup analyses will be done with the symptom of fatigue as the outcome:

Age: Younger than 65 vs 65 and older

Pre-existing mental health problems: This will be measured by self-reported current comorbidities as mental health disorder (variable mhcat____18).

Previous SARS-CoV-2 infections: Any vs none

These subgroup analyses will be done by including an interaction term between the treatment arm and the subgroup in the mixed effects proportional odds logistic regression model described above. The p-value of the subgroup by arm interaction term will be assessed to determine whether there could be a subgroup effect, with the understanding that the analysis is probably underpowered.

Measure 5.1.2

Each symptom will be assigned a score of 0 if not present, 1 if mild, 2 if moderate and 3 if severe. These scores for each symptom will be added together to get the total neurological long COVID score, ranging from 0 to 66.

Estimand

Population: Household members (older than 5 years) enrolled in the study, regardless of SARS-CoV-2 infection status (all enrolled participants)

Treatment: Initially randomised intervention to unfractionated intranasal heparin 1400u each nostril (as heparin solution 5,000u/ml, 140microL/actuation, TWO actuations each nostril) THREE times daily via a plastic nasal inhalator device or saline control and any subsequent deviations to the per protocol use of the intervention over 10 days

Outcome: Continuous neurological long COVID score (described above) at 6 months, with a 2 month window (i.e. including outcomes measured between 4 and 8 months)

Summary measure: The mean difference between arms will be reported with 95% confidence interval **Potential intercurrent events**:

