We will summarise the number of participants in each of the 4 categories of the Likert scale in each exposure group. A proportional odds logistic regression will be used to calculate the overall odds ratio, adjusted for the stratification variables and randomised arm and clustered on household. The assumption of proportional odds

will be investigated. If it is violated, we will fit a multinomial regression and calculate an odds ratio for each category.

Measure 5.1.4

In addition to assessing whether treatment assignment was associated with neurological long COVID we want to investigate whether neurological long COVID outcomes were different for participants who tested positive for SARS-CoV-2 vs those who tested negative. The research question is: Does testing positive for SARS-CoV-2 at baseline or during the 10 days of active treatment increase the severity of long COVID symptoms at 6 months?

Estimand

Population: Household members (older than 5 years) enrolled in the study, regardless of SARS-CoV-2 infection status (all enrolled participants)

Exposures compared: Tested positive for SARS-CoV-2 any time during the study (baseline positive or positive during the trial) vs tested negative for SARS-CoV-2 at all time points

Outcome: Continuous neurological long COVID score (described above) at 6 months, with a 2 month window (i.e. including outcomes measured between 4 and 8 months)

Summary measure: The mean difference between SARS-CoV-2 infected and uninfected participants will be reported with 95% confidence interval

Potential intercurrent events: None

Strategy for handling intercurrent event: Not applicable

The two exposures will be compared using mixed effects linear regression with neurological long COVID score as the outcome, adjusting for stratification factors (time from positive test to randomisation, whether the index case is a child < 5 years) randomised treatment arm and the defined baseline covariate set, with household as random effect to take the clustering by household into account.

The mean difference between the exposures will be calculated in Stata as follows using a mixed effects GLM with random intercepts:

mixed outcome i.infection_status i.arm baseline_covariates || household:

Measure 5.1.5

For participants over 16 years of age, cognition and mood were assessed using the harmonised procedures developed by the Neuro-COVID Neuropsychology International Task force. Included measures were:

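### Measure 5.1.4: the infected-versus-uninfected interval for the long COVID score relies on equal variances in two very unequal groups, and is probably too wide if infection raises the score

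*SAP*

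**What the plan says.** SAP Section 6.5, Measure 5.1.4, defines the exposure groups as follows: "Tested positive for SARS-CoV-2 any time during the study (baseline positive or positive during the trial) vs tested negative for SARS-CoV-2 at all time points". The outcome is the score from Measure 5.1.2, in which 22 symptoms rated 0 to 3 are "added together to get the total neurological long COVID score, ranging from 0 to 66". The summary measure is fixed as: "The mean difference between SARS-CoV-2 infected and uninfected participants will be reported with 95% confidence interval". The Stata command is "mixed outcome i.infection_status i.arm baseline_covariates || household", a linear model with a household random intercept. It has no `vce()` option and no residual variance by group. For this model the SAP plans no residual check, transformation or sensitivity analysis of the variance assumption.

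Measure 5.2 repeats the analysis at 12 months. Measure 5.1.6 makes the same infection comparison on the cognition and mood scales, but has no command of its own. It refers to Measure 5.1.5, which refers to Measure 4.3.

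The SAP gives no SD or distribution for the long COVID score. The relative size of the two groups is not stated either, but Section 2.6 assumes that "within household transmission will be approximately 85% in the control arm and 75% in the intervention arm", with three contacts per household.

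**The concern.** The random intercept deals with correlation within households. It does nothing about a difference in variance between infected and uninfected people. Under a common residual variance, the estimate is dominated by whichever group is larger. The standard error of a mean difference, however, is driven mainly by the smaller group. With a 1:1 split the two effects cancel, which is why the arm comparisons are hardly affected. With a split near 85:15 they do not.

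Equal variances are also doubtful in just the case the analysis is looking for. The research question of Measure 5.1.4 is whether infection increases symptom severity. For a sum score that cannot fall below 0, a group with a higher mean usually has a larger spread as well. What is at stake is the calibration of the reported 95% interval and the precision of the comparison.

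**Working it through.** **Inputs.** Section 2.6 gives contact attack rates of 85% and 75%, three contacts per index case, ICC 0.2 and 268 households (1072 people). Section 2.5 gives 1:1 allocation by household. The SD ratio is not in the SAP and is varied below as an assumption.

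**The plan's own figure.** Two proportions, 85% versus 75%, two-sided 5%, 80% power: [1.96 × √(2 × 0.80 × 0.20) + 0.8416 × √(0.85 × 0.15 + 0.75 × 0.25)]² / 0.10² = 250 per arm. Multiplied by the design effect 1 + (3 − 1) × 0.2 = 1.4, this is 350 contacts, or 117 households per arm, against the stated 120. Then 120 / 0.9 gives 134. The planning figures reproduce, so it is reasonable to project the split from them.

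**Projected split.** Infected share = (1 + 3 × attack rate) / 4, counting every index case as infected.
- Attack rate 80% (average of the arms): 0.85, that is 268 + 0.80 × 804 ≈ 911 infected and 161 uninfected.
- By arm: 0.8875 in control, 0.8125 on heparin.
- Two contacts instead of three: (1 + 2 × 0.80) / 3 = 0.87.
- Lower attack rates, assumed for range: 60% gives 0.70 and 40% gives 0.55.

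**Standard error ratio.** Let p be the infected share and r the SD ratio, infected to uninfected. Ignoring clustering, the pooled-variance standard error divided by the true one is

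√{[p r² + (1 − p)] × [1/p + 1/(1 − p)] / [r²/p + 1/(1 − p)]} = √{[p r² + (1 − p)] / [(1 − p) r² + p]}.

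Nominal 95% coverage becomes 2Φ(1.96 × ratio) − 1.

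| p | r | ratio | coverage |
|---|---|---|---|
| 0.85 | 0.8 | √(0.694 / 0.946) = 0.86 | 90.7% |
| 0.85 | 1 | 1.00 | 95.0% |
| 0.85 | 1.25 | √(1.478 / 1.084) = 1.17 | 97.8% |
| 0.85 | 1.5 | √(2.0625 / 1.1875) = 1.32 | 99.0% |
| 0.85 | 2 | √(3.55 / 1.45) = 1.57 (1.565) | 99.8% |
| 0.70 | 1.5 | √(1.875 / 1.375) = 1.17 | 97.8% |
| 0.55 | 1.5 | √(1.6875 / 1.5625) = 1.04 | 95.8% |
| 0.50 | any | 1.00 | 95.0% |

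**Simulation with clustering.** 241 households of four (268 less 10%), contact infection with ICC 0.2, overdispersed counts bounded at 0 and capped at 66, random-intercept maximum likelihood adjusted for infection and arm, 2000 runs per row. The means and dispersion are assumptions.

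| mean uninfected / infected | variance ratio | coverage, model-based | coverage, household-robust |
|---|---|---|---|
| 5 / 5 | 1.0 | 95.6% | 94.2% |
| 4 / 5 | 1.5 | 97.2% | 94.2% |
| 3 / 5 | 2.6 | 99.1% | 94.6% |
| 3 / 6 | 3.5 | 99.6% | 95.0% |
| 2 / 6 | 7.5 | 99.9% | 94.7% |
| 6 / 4 | 0.48 | 88.1% | 94.3% |

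For 4 versus 5 the model-based standard error was 0.645 against an empirical 0.573, and power was 34% model-based against 48% robust. For 5 versus 5 the type I error was 4.5% and 5.7%. A second simulation (268 households, uninfected mean 3, 32% to 40% zeros, also assumed) gave power of 40% against 55% for a one-point difference, and type I error of 5.4% and 6.5% with no effect.

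**The case against.** A reader might infer that an uneven split plus a floor at 0 makes the planned interval simply wrong. The SAP does not support that. Unequal variances are also needed, and the SAP gives no SD from which to judge them. With equal variances the interval is close to nominal, as the first simulation row shows. In the direction the SAP asks about, the error is conservative: it costs precision and creates no false positives. An interval that is too narrow needs the small uninfected group to be the more variable one, which runs against the floor argument unless infection lowers the score. All of this stands and limits the point.

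The split is also a projection. It applies sample-size attack rates to everyone enrolled and counts every index case as PCR positive, although Section 5.1 allows for households with no positive swab on day 1. The analysed group is further restricted to participants older than 5 years who were assessed at 4 to 8 months. At 55% infected the inflation nearly vanishes. This stands too, and is why a range is given.

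Nor is the missing option an internal contradiction. The robust variance in Section 5.1, "xtpoisson outcome i.arm baseline_covariates, re vce(robust) irr", serves a Poisson model for a binary outcome, where the model-based variance cannot be right. The SAP's `mixed` commands are model-based throughout.

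A reader might also look to the p-value in Table 23. That table belongs to Measure 5.1.6. Measure 5.1.4 is reported in Table 21, which has only a confidence interval.

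Finally, Measure 5.1.3 compares the same groups by proportional odds, with an assumption check and a fallback. It does so symptom by symptom, so it does not protect the interval for the total score.

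**Conclusion.** The point holds in conditional form. As written, calibration of the Measure 5.1.4 interval depends on an equal-variance assumption that the SAP neither states nor checks, and that is implausible if infection has the effect under study. The likely consequence is an interval that is too wide: 17% to 32% at 85:15 for assumed SD ratios of 1.25 to 1.5, and 4% to 17% at 55% to 70% infected for an SD ratio of 1.5. In the simulated cases with a one-point effect, the loss of power was about 15 percentage points, but that figure rests on assumed means and dispersion.

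The same holds for the 12-month repeat. The case is weaker for Measure 5.1.6, because the SAP gives no range or floor for those scales. The comparison is secondary and non-randomised, and the SAP claims no power for it, so this is an inexpensive improvement and not a threat to the trial's conclusions.

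**What to change.** Keep the Measure 5.1.4 command and end it, after the household term, with `:, vce(cluster household)`. Use the same option for the infection-status comparisons in Measure 5.1.6 and for the 12-month repeats of both under Measure 5.2. The 1:1 arm comparisons (Measures 4.3, 5.1.2 and 5.1.5) do not need it.

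The cost is one option in the Stata code. The downside is slightly more variable standard errors in small samples, which is negligible with about 240 to 268 households: robust coverage was 94.2% to 95.0% in the tabulated simulation and about 93.5% to 96% in the other.

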Index case in the household not taking study drug. This is defined as compliance <90% Participant (this household member) not taking study drug. This is defined as compliance <90% Either participant (this household member) or index case stop treatment due to adverse event Participant received an anti-viral

Strategy for handling intercurrent event:

All intercurrent events will be handled through the treatment policy strategy, which means that the intercurrent events will be ignored.

Treatment arms will be compared using mixed effects linear regression with maximum symptom severity as the outcome, adjusting for stratification factors (time from positive test to randomisation, whether the index case is a child < 5 years), participant age, inhaled steroid use at baseline, days since symptom onset at randomisation, whether there are children in the household and household size (referred to as the defined baseline covariate set), with household as random effect to take the clustering by household into account.

The mean difference between the treatment arms will be calculated in Stata as follows using a mixed effects GLM with random intercepts:

mixed outcome i.arm baseline_covariates || household:

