- Cognitive screening using Telephone Montreal Cognitive Assessment (T-MoCA) Total Score
- Subjective cognitive complaints using Patient's assessment of Own Functioning Inventory (PAOFI) Total
 - o Memory
 - Language and communication
 - Use of hands
 - \circ Sensory-perception
 - o Higher-level cognitive and intellectual functions
 - Work/recreation
- Attention/working memory using the Wechsler Adult Intelligence Scale (WAIS) digit span
 - Digit Span Forward
 - $\,\circ\,$ Digit Span Backward
- Mood using the Depression, Anxiety and Stress Scales (DASS)
 - \circ Depression
 - o Anxiety
 - o Stress

For each of the tests and scales listed above we will calculate the following estimand:

Estimand

Population: Household members (older than 16 years) enrolled in the study, regardless of SARS-CoV-2 infection status (all enrolled participants)

Treatment: Initially randomised intervention to unfractionated intranasal heparin 1400u each nostril (as heparin solution 5,000u/ml, 140microL/actuation, TWO actuations each nostril) THREE times daily via a plastic nasal inhalator device or saline control and any subsequent deviations to the per protocol use of the intervention over 10 days

Outcome: Each continuous scale measuring cognition or mood as listed above at 6 months, with a 2 month window (i.e. including outcomes measured between 4 and 8 months)

Summary measure: The mean difference between arms will be reported with 95% confidence interval **Potential intercurrent events**:

Index case in the household not taking study drug. This is defined as compliance <90% Participant (this household member) not taking study drug. This is defined as compliance <90% Either participant (this household member) or index case stop treatment due to adverse event Participant received an anti-viral

Strategy for handling intercurrent event:

All intercurrent events will be handled through the treatment policy strategy, which means that the intercurrent events will be ignored.

The same analysis as described for Measure 4.3 will be done.

This analysis will also be repeated in the subgroup of participants who had SARS-CoV-2 infection.

Measure 5.1.6

In addition to assessing whether treatment assignment was associated with neurological long COVID we want to investigate whether neurological long COVID outcomes were different for participants who tested positive for SARS-CoC-2 vs those who tested negative.

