For each of the scales listed in Measure 5.1.5 we will also calculate the following estimand:

Estimand

Population: Household members (older than 16 years) enrolled in the study, regardless of SARS-CoV-2 infection status (all enrolled participants)

Exposures compared: Tested positive for SARS-CoV-2 any time during the study (baseline positive or positive during the trial) vs tested negative for SARS-CoV-2 at all time points

Outcome: Each continuous scale measuring cognition or mood as listed in Section 5.1.5 at 6 months, with a 2 month window (i.e. including outcomes measured between 4 and 8 months)

Summary measure: The mean difference between SARS-CoV-2 infected and uninfected participants will be reported with 95% confidence interval

Potential intercurrent events: None

Strategy for handling intercurrent event: Not applicable

The same analysis as described in Measure 5.1.5 will be done.

Measure 5.2

Number of participants with clinical symptoms of neurological long COVID at 12 months post participation in trial.

The measures done at 6 months will be repeated at 12 months. The same analyses as described for 6 months (Measures 5.1.1 to 5.1.6) will be repeated at 12 months.

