Table 21: Secondary outcome 5.1.4. Neurological long COVID at 6 months. Continuous neurological longCOVID score

Heparin	Placebo	Mean difference (95% CI)

Table 22: Secondary outcome 5.1.5. Neurological long COVID at 6 months

Scale	Mear	n (95% CI)	Mean difference between arms (95% CI)	p-value
	Heparin	Placebo		
e.g. WAIS digit span				
DASS etc				
Repeat for subgroup of participants SARS-CoV2 positive				

Table 23: Secondary outcome 5.1.6. Neurological long COVID at 6 months.

Scale	Mean (95% CI)		Mean difference (95%	p-value
			CI)	
	SARS-	SARS-CoV-		
	CoV-2	2 negative		
	positive			
e.g. WAIS digit span				
DASS etc				
Repeat for subgroup of participants SARS-CoV2				
positive				

Table 24: Secondary outcome 5.1.6. Neurological long COVID at 6 months. Subgroup analysesRepeat Table 22 for each subgroup, also include p-value for subgroup

Table 25: Secondary outcome 5.2.1. Neurological long COVID at 6 months. Presence of symptomsRepeat Table 17

Table 26: Secondary outcome 5.2.1. Neurological long COVID at 6 months. Presence of symptoms insubgroup of participants who had SARS-CoV-2 infectionRepeat Table 18

Table 27: Secondary outcome 5.2.2. Neurological long COVID at 6 months. Continuous neurological long COVID score

Repeat Table 19

Table 28: Secondary outcome 5.2.3. Neurological long COVID at 6 months. Presence of symptomsRepeat Table 20

Table 29: Secondary outcome 5.2.4. Neurological long COVID at 6 months. Continuous neurological long COVID score Repeat Table 21

Table 30: Secondary outcome 5.2.5. Neurological long COVID at 6 months.Repeat Table 22

Table 31: Adverse events

	Heparin n (%)	Placebo n (%)
Major bleed		
Nasal itching		
Nose bleed		
HIT		
Local nasal irritation		
Loal or generalized oedema		
Thrombosis		
Sneezing		
Other		
Serious adverse events		
Mean duration of nose bleeds

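### Measure 5.1.6 asks for infected versus uninfected, but its cross-reference ends in a model with no infection term

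*SAP*

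**What the plan says.** SAP Section 6.5 has two kinds of neurological long COVID comparison. Measures 5.1.1, 5.1.2 and 5.1.5 compare the randomised arms. Measures 5.1.3, 5.1.4 and 5.1.6 compare participants who tested positive with those who tested negative.

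For Measure 5.1.6 the contrast begins "Exposures compared: Tested positive for SARS-CoV-2 any time during the study (baseline positive or positive during the trial", and the summary measure is the infected-minus-uninfected mean difference with a 95% confidence interval. The analysis line is "The same analysis as described in Measure 5.1.5 will be done". Under Measure 5.1.5 the analysis line is "The same analysis as described for Measure 4.3 will be done". Section 6.4 gives the Measure 4.3 model as "mixed outcome i.arm baseline_covariates || household".

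For the parallel Measure 5.1.4, which makes the infection comparison on the total symptom score, the SAP writes out a different model: "mixed outcome i.infection_status i.arm baseline_covariates || household".

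Measure 5.2 repeats all six 6-month measures at 12 months. Section 8 provides the shells, among them "Table 21: Secondary outcome 5.1.4. Neurological long COVID at 6 months. Continuous neurological longCOVID score" and "Table 30: Secondary outcome 5.2.5. Neurological long COVID at 6 months".

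**The concern.** An analyst who follows the references for 5.1.6 arrives at a model whose only comparison term is treatment arm. That gives a second copy of the 5.1.5 result, and the quantity that 5.1.6 defines is never estimated. The question at stake is whether infection is associated with worse cognition or mood at 6 and 12 months. If the contradiction is found only at the analysis stage, the model for that question has to be chosen after the data are in hand.

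The shells add to the confusion. For 5.1.4 the model is right and the shell is wrong; for 5.1.6 the shell columns are right and the model reference is wrong. Neither the text nor the tables can be taken as the consistently correct source.

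**Working it through.** No stated figure of the plan is involved, so the check is mainly a trace of references.

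**Step 1: follow the chain.** 5.1.6 refers to 5.1.5, 5.1.5 refers to 4.3, and 4.3 has arm, the baseline covariates and a household random effect. Section 3.9 defines those covariates as the two stratification factors, participant age, inhaled steroid use, days since the index case's symptom onset, children in the household and household size. Infection status is not among them, so the chain ends without an infection coefficient.

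**Step 2: set the measures side by side.**

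| Measure | Contrast in the estimand | Model reached | Shell columns |
|---|---|---|---|
| 5.1.3 | infection | infection groups compared, adjusted for arm (ordinal) | Table 20: positive, negative |
| 5.1.4 | infection | infection status plus arm | Table 21: heparin, placebo |
| 5.1.5 | arm | arm | Table 22: heparin, placebo |
| 5.1.6 | infection | arm only | Table 23: positive, negative |

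Two cells disagree with their own row: the model for 5.1.6 and the shell for 5.1.4. Table 29 (5.2.4) repeats Table 21 and inherits its columns.

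**Step 3: the extra row in Table 23.** This shell also asks for a repeat among SARS-CoV-2 positive participants. Measure 5.1.5 has such a repeat, and there it makes sense because both arms contain positive participants. In an infected-versus-uninfected table the restriction removes the whole uninfected group, so no difference can be computed.

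**Step 4: count what is affected.** Measure 5.1.5 lists T-MoCA total (1), PAOFI total (1) with six domains (6), digit span forward and backward (2) and three DASS scales (3): 1 + 1 + 6 + 2 + 3 = 13 scores. At two time points that is 13 × 2 = 26 results.

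**Step 5: illustrate what each model returns.** Inputs from SAP Section 2.6: 268 households of 4, with contact infection of 85% (control) and 75% (intervention). Assumed, not from the SAP: index cases all infected, an infection effect of +2 points, no direct arm effect, household SD 1.5, residual SD 4, no covariates; 60 simulated trials.

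- Model with arm only (the one 5.1.6 reaches): mean arm coefficient −0.16, no infection coefficient. By hand, three of four members are contacts, so the arms differ in infection by 0.75 × (0.75 − 0.85) = −0.075, and −0.075 × 2 = −0.15, which agrees.
- Model with infection status and arm (the one for 5.1.4): mean infection coefficient 1.97 against a true 2, mean arm coefficient −0.01.

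The arm-only model thus answers a different question. The sizes depend on the assumed inputs and predict nothing about this trial.

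**Step 6: the 12-month shells.** Tables 25 to 30 carry 5.2.x numbers, which Measure 5.2 defines as 12 months, yet all six titles say 6 months. The list stops at 5.2.5, so 5.2.6 has no shell.

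**The case against.** The strongest reply is that only one sentence is wrong. The purpose statement, the exposure definition, the summary measure and the Table 23 columns of 5.1.6 all state infected versus uninfected. An arm coefficient cannot fill Table 23, and a suitable model stands two measures earlier. This stands: it makes the point an internal contradiction with a recoverable intent, not a plan that consistently specifies the wrong analysis. It does not remove the need for correction, because the one sentence is the only analysis instruction that 5.1.6 has.

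A reader might infer more in three ways that the SAP does not support.

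- **That 5.1.4 also yields the arm comparison.** It does not. Its prose and Stata line both contain infection status; only the columns of Tables 21 and 29 are wrong.
- **That a late positive test could count as exposure for a 6-month outcome.** The exposure line is loosely worded, but the 5.1.4 research question reads "Does testing positive for SARS-CoV-2 at baseline or during the 10 days of active treatment increase the severity of long COVID symptoms at 6 months". Section 6 applies the Section 3.8 algorithm to all secondary outcomes that refer to SARS-CoV-2 status. Section 3.8 relies in general on provider-collected PCR, and Section 2.7 schedules those swabs before treatment and on days 3, 5 and 10.
- **That barely swabbed people enter the uninfected group and dilute the difference.** The comparison group must have tested negative at all time points, which does not literally admit someone with most swabs missing. The SAP gives no missing-swab rate from which to size any dilution.

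It is also fair to say that the 12-month titles and the absent 5.2.6 shell are clerical. The table numbering shows what is meant, and Measure 5.2 orders the analysis with or without a shell.

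**Conclusion.** The point holds for Measure 5.1.6: its analysis instruction cannot produce its own summary measure. It affects 13 scores at each of two time points, 26 results in all. That count takes PAOFI as a total plus six domains, and digit span and DASS by their listed parts. For Measure 5.1.4 the fault is confined to the display in Tables 21 and 29, and the positive-only row in Table 23 cannot be filled. These are secondary, non-randomised comparisons. The primary analysis and every between-arm analysis stand as written. It should be corrected before analysis, but it does not threaten the trial's main conclusions.

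**What to change.** 1. In Measure 5.1.6, replace the reference to Measure 5.1.5 with one to Measure 5.1.4, so that the model is "mixed outcome i.infection_status i.arm baseline_covariates || household". Measure 5.2 then carries the correction to 12 months.
2. Give Table 21, and Table 29 which repeats it, SARS-CoV-2 positive and negative columns in place of heparin and placebo. Leave the 5.1.4 model as it is.
3. Delete the positive-only repeat row from Table 23.
4. As clerical tidying, retitle Tables 25 to 30 as 12 months and add a shell for 5.2.6 modelled on the corrected Table 23.

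The cost is a few lines of SAP and shell text. No data, population, sample size or between-arm result changes.
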